5.1 Study Design (SAD)

This is a 6-cohort, single site, first-in human, double-blind, placebo-controlled, randomized single ascending dose (SAD) study assessing (2R,6R)-Hydroxynorketamine in healthy male and female volunteers. All Subjects in the SAD study will undergo a screening period of up to 28 days to ensure that all eligibility requirements are met. Key baseline safety metrics will be taken during screening and on the first Day of

confinement. Selected safety metrics will be collected during the on-drug portion of the study. A final safety assessment will be conducted via an outpatient visit and follow-up phone call.

All cohorts will include 6 Subjects receiving drug and 2 Subjects receiving placebo. All cohorts will incorporate sentinel dosing of 1 active and 1 placebo Subject. Each Subject will only participate in a single dose level. Table 1 outlines the planned dosing levels and number of Subjects in each cohort.

Each treatment will be administered after Subjects have fasted overnight for at least 8 hours.

rable 1: SAD plained dosing levels								
	Dose	Subjects on	Subjects on					
Cohort	(mg/kg)	Active Drug (n)	Placebo (n)					
1A (Sentinel 1)	0.1	1	1					
1B	0.1	5	1					
2A (Sentinel 2)	0.25	1	1					
2B	0.25	5	1					
3A (Sentinel 3)	0.5	1	1					
3B	0.5	5	1					
4A (Sentinel 4)	1.0	1	1					
4B	1.0	5	1					
5A (Sentinel 5)	2.0	1	1					
5B	2.0	5	1					
6A (Sentinel 6)	4.0	1	1					
6B	4.0	5	1					

Table 1: SAD planned dosing levels

5.2 Study Design (MAD)

The multiple ascending dose (MAD) portion of the study is a 2-cohort single site, doubleblind, placebo-controlled design assessing (2R,6R)-Hydroxynorketamine in healthy male and female volunteers. All Subjects in the MAD study will undergo a screening period of up to 28 days to ensure that all eligibility requirements are met. Key baseline safety metrics will be taken during screening and on the first Day of confinement. Selected safety metrics will be collected during the on-drug portion of the study. A final safety assessment will be conducted via an outpatient visit and follow-up phone call.

All cohorts will include 6 Subjects receiving drug and 2 Subjects receiving placebo. Each Subject will receive a total of 4 doses (drug or placebo) administered on days 1, 4, 8, and 11. Each Subject will only participate in a single dose level. Table 2 outlines the planned dosing levels and number of Subjects in each cohort.

Each dose will be administered after Subjects have fasted overnight for at least 8 hours.

Table 2: MAD planned dosing levels

Dose Cohort (mg/kg)		Subjects on	Subjects on Placebo (n)	
1	1.0	Active Drug (n) 6	2	
2	2.0	6	2	

5.3 Study Design (CSF)

The single dose capture study (CSF) portion of the study is a 2-cohort single site, doubleblind, placebo-controlled design assessing (2R,6R)-Hydroxynorketamine in healthy male and female volunteers. All Subjects in the CSF study will undergo a screening period of up to 28 days to ensure that all eligibility requirements are met. Key baseline safety metrics will be taken during screening and on the first Day of confinement. Selected safety metrics will be collected during the on-drug portion of the study. A final safety assessment will be conducted via an outpatient visit and follow-up phone call.

All cohorts will include 5 Subjects receiving drug and 3 Subjects receiving placebo. Each Subject will only participate in a single dose level. Table 3 outlines the planned dosing levels and number of Subjects in each cohort.

Each dose will be administered after Subjects have fasted overnight for at least 8 hours.

Table 3: CSF planned dosing levels

Cohort	Dose	Subjects on	Subjects on
	(mg/kg)	Active Drug (n)	Placebo (n)
1	0.25	5	3

5.4 Selection of Study Population

Healthy male and female adult subjects (18-65 years old) will be enrolled in this study. It is expected that the PK of (2R,6R)-Hydroxynorketamine in these Subjects will be representative of the PK profile in patients with TRD. The cohort size in all SAD and MAD stages is expected to sufficiently evaluate the safety and PK of (2R,6R)-Hydroxynorketamine. Furthermore, these cohort sizes are also expected to provide sufficient qEEG data to evaluate the use of qEEG as a potential PD biomarker. Analysis of qEEG is not included as part of the proposed Statistical Analysis Plan (SAP).

5.5 Treatment Assignment

5.5.1 Randomization Procedures

All Subjects and clinical staff, (except the unblinded pharmacy staff) will be blinded to treatment. An unblinded pharmacist staff will be required at the Clinical Site to comply with the study's randomization and blinding requirements. At the clinical site, prior to study administration, the PI will be responsible for designating a qualified pharmacy staff

to serve as the unblinded pharmacy staff in the study. Unblinded pharmacy staff may dose Subjects, but may not participate in Subject assessments.

The designated, unblinded pharmacy staff will be responsible for all drug accountability issues, including preparing, labelling, and dispensing study drug and placebo in accordance with the randomization codes provided, yet remain independent of all Subject assessments. The pharmacy staff will follow the Standard Operating Procedures and Work instructions related to pharmacy services and protocol-specific requirements.

Randomization codes will be provided to the unblinded pharmacy staff. Confirmation of receipt of the randomization code will be required by the Sponsor. The unblinded pharmacy staff will be responsible for maintaining the blind, consistent with protocol design, throughout the study. All documentation is to be filed in the Pharmacy Manual. Access to this manual will be restricted to the unblinded pharmacy staff.

The Subjects, PI, and all other study personnel involved with the Subject assessments will be blinded to the actual treatment assignment of the Subjects. The PI will be ultimately responsible for ensuring the integrity of the blind, and that it is maintained through the study.

The treatment assignment should only be unblinded at the clinic in the case of dose limiting toxicity or emergency when the knowledge of the study drug assignment is necessary for the clinical management or welfare of the Subject. Breaking the blind at the clinic under any other circumstance will be considered a protocol violation. The PI is strongly encouraged to contact the sponsor before unblinding the study drug assignment. If the blind is broken for any reason, the Investigator must notify the Sponsor within one day. In addition, the Investigator will record the date and reason for revealing the blinded study drug assignment for that Subject in the source documents and appropriate case report form page(s).

6. Populations for Analysis

6.1 Randomized Population

All participants who are randomized to treatment assignment.

6.2 Safety Population

All participants who received at least one dose of study medication. This includes any subjects who were replaced and received at least one dose.

6.3 PK Population

All participants who have at least one interpretable PK sample. PK population will be further defined in the PK Analysis Plan

6.4 qEEG Population

qEEG population will be defined in the qEEG Analysis Plan.

6.5 On Treatment Population

All participants who completed all doses for their treatment group.

7. General Analysis Conventions

Analyses will be stratified by treatment assignment, dose groups, and sub studies (SAD, MAD, CSF):

- SAD
 - Cohorts 1 through 6 (2R,6R)-Hydroxynorketamine individually
 - Overall (2R,6R)-Hydroxynorketamine
 - Overall placebo
- MAD
 - Cohorts 1 through 2 (2R,6R)-Hydroxynorketamine individually
 - Overall (2R,6R)-Hydroxynorketamine
 - Overall placebo
- CSF
 - Cohort 1 (2R,6R)-Hydroxynorketamine individually
 - o Overall placebo

General statistical approaches are presented below.

All subjects in the Safety Population will be included in the safety analysis grouped by study, cohort, and treatment group. Statistical analysis of safety data will be descriptive.

Baseline is defined as the last non-missing assessment prior to dosing of study medication.

For continuous variables, summaries will include sample size, mean, median, 25th and 75th percentiles, standard deviation, minimum, and maximum. For categorical variables, the summaries will include frequencies and corresponding percentages. No inferential hypothesis testing will be performed. Repeat or unscheduled results will not be included in the summaries, but will be listed. Data from placebo subjects will be pooled for final presentations.

Missing data results will not be imputed. Data summaries and analyses (e.g. means) will be calculated using all available data. If the start day for an AE is missing, day of study drug administration will be used and AE will be considered treatment emergent. Neither month nor year will be imputed for AE.

Planned analyses are descriptive or exploratory. If presented, significance level and confidence intervals will use alpha of 0.05. No adjustments for multiple testing are planned.

Analyses will be performed using a UNIX server based installation of SAS Software, version 9.4 or newer.

8. Outcomes

8.1 Primary Outcome Measures

Study outcomes include

- Completion of all dosing levels and timepoints with full collection of all safety data
- Adverse event (AE) tabulation
- Clinical laboratory tests

8.2 Secondary Outcome Measures

8.2.1 Pharmacokinetics

Analysis of this outcome will be covered by the separate PK Analysis Plan.

8.2.2 qEEG

Analysis of this outcome will be covered by the separate qEEG Analysis Plan.

9. Analysis Endpoints

9.1 Primary Endpoints

The primary endpoints are the following:

- 1) Study Drug Exposure
- 2) Concomitant Medications
- 3) Safety Analysis
- 4) Adverse Events
- 5) Clinical Laboratory Results
- 6) Vital Signs
- 7) Physical Examinations
- 8) Ocular Examinations
- 9) Mood and Cognitive Assessment (POMS)
- 10) Suicide Screen (C-SSRS)
- 11) Clinician Administered Dissociative States Scale
- 12) Modified Observer's Assessment of Alertness/Sedation Scale (MOASS)

9.2 Pharmacodynamics Endpoints

A second primary objective for this study is to assess the pharmacokinetics (PK) of (2R,6R)-Hydroxynorketamine HCl. PK endpoint analyses are covered in the PK analysis plan.

9.3 qEEG Endpoints

The secondary objective of this study is to collect quantitative electroencephalography (qEEG) data as a PD biomarker. qEEG endpoint analyses are covered in the qEEG analysis plan.

10. Sample Size

A total of 48 Subjects are planned to be enrolled in a 6-cohort SAD study (36 in the treatment groups and 12 in the control groups).

All SAD cohorts will have 6 Subjects in the treatment group and 2 Subjects in placebo group. All cohorts in the SAD study will incorporate sentinel dosing which will include 1 active and 1 placebo Subject. All remaining Subjects will be dosed at least 24 hours after the sentinel cohort participants.

A total of 16 Subjects are planned to be enrolled in a 2 cohort MAD study (12 in the treatment groups and 4 in the control groups). All MAD cohorts will have 6 Subjects in the treatment group and 2 Subjects in placebo group.

A total of 8 subjects are planned to be enrolled in a 1 cohort CSF capture study. The CSF cohort will have 5 in the treatment group and 3 in the control group.

Additional cohorts (both SAD and MAD) may be enrolled if it is determined that an intermediate or higher dose level should be evaluated upon review of both safety and PK data. The Institutional Review Board will be notified of this revised approach.

11. Analyses and Reporting

11.1 Final Analyses

All final, planned analyses identified in this SAP will be performed only after the last participant has completed the last study visit, safety period and had end of study assessments, and all relevant study data have been processed and integrated into the analysis database. In addition, no database may be locked or analyses completed until this SAP has been approved. Unblinding of treatment assignments will not occur until the data are locked.

12. Planned Analyses

The Safety Population will be used for all analyses unless otherwise specified.

12.1 Subject Disposition

Analysis populations will be summarized by study (SAD/MAD/CSF), cohort, and treatment assignment. The Safety Population will be used for any additional Subject Disposition analyses.

The number and percentage of subjects who completed and prematurely discontinued the study will be presented by study drug and overall vs placebo for the Randomized Population. Reasons for premature discontinuation as recorded on the completion page of the CRF will be summarized, as applicable.

12.2 Demographics and Baseline Characteristics

The Safety Population will be used for Demographic and Baseline Characteristics analyses.

Demographic and baseline characteristics (e.g. age, weight) will be summarized and listed by study cohort and treatment assignment.

Medical history will be summarized by system organ class and preferred term. Terms will be coded using MedDRA 23.1 or higher. Terms will also be listed, including verbatim term and condition onset date.

12.3 Study Drug Exposure

The Safety Population will be used for all Study Drug Exposure analyses.

Study drug exposure will be summarized by study (SAD/MAD/CSF), treatment assignment, and dose group. Individual patient listings will also be provided.

12.4 Concomitant Medications

Concomitant medications will be listed, along with available information on dose, route, frequency, and used to treat AE. Terms will be coded using B3 WHO Drug General.

12.5 Safety Analyses

The Safety Population will be used for all safety analyses unless otherwise indicated. All analyses will include summaries by treatment group and study cohort. All summaries will be supported by data listings.

12.6 Adverse Events

An adverse event (AE) is any untoward medical occurrence in humans, whether or not considered drug-related, which occurs during the conduct of a clinical trial. (Any change in clinical status, routine labs, x-rays, physical examinations, etc.), that is considered clinically significant by the study investigator is considered an AE. All AEs will be coded using the Medical Dictionary for Regulatory Activities (MedDRA) central coding dictionary.

Adverse reaction is any adverse event caused by the drug. Suspected adverse reaction is any adverse event for which there is a reasonable possibility that the drug caused the adverse event. A reasonable possibility implies that there is evidence that the drug caused the event. An event will be considered Related to study drug if the investigator deems the event relationship as Possible, Probably, or Definite. An event is Not Related if the investigator classified the event relationship to study drug as Unlikely or Not Related. Expectedness and Severity (Mild, Moderate, Severe) of event will also be collected.

An AE or Suspected Adverse Reaction (SAR) or Adverse Reaction is considered "Serious" if, in the view of either the investigator or sponsor, it results in any of the following outcomes:

- Results in death
- Is life-threatening (places the subject at immediate risk of death from the event as it occurred)
- Results in inpatient hospitalization or prolongation of existing hospitalization
- Results in a persistent or significant disability or incapacity
- Results in a congenital anomaly or birth defect
- An important medical event that may not result in death, be life threatening, or require hospitalization may be considered a serious adverse event (SAE) when, based upon appropriate medical judgment, the event may jeopardize the subject and may require medical or surgical intervention to prevent one of the outcomes listed in this definition.

12.7 Clinical Laboratory Results

Summary statistics of observed and change from baseline data will be presented for each treatment group, cohort, and dose where applicable. Shift tables summarizing the numbers of subjects shifting from normal pre-dose values to abnormal post-dose values will also be presented where applicable.

Lab tests included will be all in the hematology and coagulation panel, biochemistry panel, and urinalysis panel (as needed lab tests: RBC, WBC, hyaline casts, cellular casts, and granular casts will only be presented as listings).

Listings for all safety laboratory evaluations will also be presented.

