#### **9.2 INCLUSION CRITERIA**

All volunteers must satisfy the following criteria to be considered for study participation.

- 1. Be a healthy male or female between 18 and 65 years of age (inclusive).
- 2. Voluntarily consents to participate in the study and provides written informed consent before the start of any study-specific procedures.
- 3. Be willing and able to remain in the study unit for the entire duration of the confinement period and return for outpatient visits.
- 4. Agree to comply with prohibitions and restrictions (section 9.5).
- 5. Females must have a negative serum β-human chorionic gonadotropin (hCG) pregnancy test at screening and a negative urine pregnancy test on Day -1 prior to study initiation.
- 6. Females must be of nonchildbearing potential or agree to use appropriate birth control, as defined in section 9.4 Contraception Requirements.
- 7. Males must be surgically sterile for at least 90 days before screening or agree to use a condom with spermicide when sexually active with a female partner who is not using an acceptable form of birth control during the study and for 90 days after study administration. Males must also agree to not donate sperm starting at enrollment and for 90 days after last study drug administration.
- 8. BMI (weight [kg]/[m^2]) between 18 and 35 kg/m^2 (inclusive) and weighs between 50 and 120 kg (110 264 pounds), inclusive.
- Blood pressure (after Subject is in a supine position for approximately 5 minutes) between 90 and 145 mmHg systolic (inclusive) and no higher than 90 mmHg diastolic at Screening and Day -1.
- 10. A 12-lead ECG with no clinically significant abnormality as judged by the Investigator and QTcf interval ≤ 450 milliseconds at Screening and Day -1.
- 11. Resting pulse rate between 45 and 100 beats per minute at Screening and Day -1.
- 12. Clinical laboratory findings and VS within normal range, or if outside of the normal ranges, deemed not clinically significant in the opinion of the Investigator.
- 13. Agree to comply with the rules regarding consumption of alcohol, caffeinated beverages, and tobacco/nicotine products during the study.

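### SAP 12.7 builds its laboratory shift tables only from normal baselines, so when an analyte is already out of range before dosing, a later flip or further worsening is not tabulated

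*SAP*

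**What the plan says.** SAP 12.7 plans three laboratory outputs.

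- Descriptive statistics: "Summary statistics of observed and change from baseline data will be presented for each treatment group, cohort, and dose where applicable".
- Shift tables: "Shift tables summarizing the numbers of subjects shifting from normal pre-dose values to abnormal post-dose values will also be presented where applicable". No other shift is described. The section does not say whether an abnormal post-dose value is classed as low or high, whether it is taken visit by visit or as the worst value, or what the denominator is.
- Listings: "Listings for all safety laboratory evaluations will also be presented".

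Four other places bear on this.

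- Protocol 9.2, criterion 12, requires laboratory findings to be in the normal range, "or if outside of the normal ranges, deemed not clinically significant in the opinion of the Investigator".
- SAP section 7 (General Analysis Conventions) fixes the reference point: "Baseline is defined as the last non-missing assessment prior to dosing of study medication". It also sets the continuous summaries, which include minimum and maximum, and says of the analysis as a whole: "No inferential hypothesis testing will be performed".
- SAP 9.1 lists "5) Clinical Laboratory Results" among the primary endpoints, and SAP 8.1 names clinical laboratory tests as a primary outcome.
- SAP 12.6 covers changes in routine laboratory tests: a change "that is considered clinically significant by the study investigator is considered an AE".

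**The concern.** The shift table is the only planned output that follows a subject from one laboratory category to another. As worded, it admits only subjects who start in range. The eligibility criteria expect that some will not. For those subjects and that analyte, a move from low to high, from high to low, or from slightly high to far above the limit adds nothing to the table.

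Direction is the second gap. For potassium, sodium, glucose, white cells and platelets, a low and a high result are different safety findings. For AST and ALT, a fall below range is not the same finding as a rise. The SAP wording does not commit to keeping them apart.

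The safety analysis is descriptive, so the tables are the result. With 6 active subjects in each SAD and MAD cohort, one subject is 17% of the group (1/6), and an analyte's table can look cleaner than the data behind it.

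**Working it through.** The documents give no figure to reproduce here, so the check is mainly one of wording.

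**Step 1: what the table covers.** Cross baseline (low, normal, high) with post-dose (low, normal, high). That gives 3 × 3 = 9 cells per analyte. The SAP wording covers 2: normal to low and normal to high. It does not cover low to high, high to low, or the two persistently abnormal cells (low to low, high to high), where further worsening would sit.

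**Step 2: can a subject be in an uncovered row?** Yes. Criterion 12 admits such subjects. The SAP baseline is the last value before dosing, and Protocol Tables 9 to 11 schedule a clinical laboratory draw before the first infusion on Day 1, after eligibility is confirmed on Day -1 (Protocol 9.1). The baseline can therefore be a value that the eligibility check did not use.

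**Step 3: what do the other outputs show?**
- Change-from-baseline statistics include the largest rise and fall in each group. They do not show whether that subject began in range or crossed a limit.
- Urine dipstick results such as protein and blood, if recorded as categories, receive only frequencies and percentages under SAP section 7. The shift table would then be the only summary of within-subject change.
- Listings hold every value but do not count shifts by dose group or against placebo.
- AE tables are by dose, but count only changes that the investigator judges clinically significant.

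**Step 4: scale (illustration only).** Assume a proportion r of subjects is out of range at baseline on a given analyte. The documents give no r, so take 1% to 10%. For an active SAD or MAD group of 6, one analyte at a time:

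P(at least one subject outside that analyte's table) = 1 − (1 − r)^6

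| r | Calculation | Result |
|---|---|---|
| 1% | 1 − 0.99^6 | 6% |
| 2.5% | 1 − 0.975^6 | 14% |
| 5% | 1 − 0.95^6 | 26% |
| 10% | 1 − 0.90^6 | 47% |

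**Step 5: a missed worsening is rarer.** It needs an abnormal baseline and then a worsening. Let w be the proportion of such subjects who worsen (also assumed). Then P = 1 − (1 − r × w)^6.

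- At r = 5%: w = 10% gives 1 − 0.995^6 = 3%; w = 25% gives 1 − 0.9875^6 = 7%; w = 50% gives 1 − 0.975^6 = 14%.
- At the corners: r = 1%, w = 10% gives 1 − 0.999^6 = 0.6%; r = 10%, w = 50% gives 1 − 0.95^6 = 26%.

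**The case against.** The best defence is that this is the layout of one table and that nothing is lost. That is largely right.

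- A reader might infer that a single large change among 6 subjects would be hidden behind a mean or median. SAP section 7 rules that out: minimum and maximum are required, so the extreme change is printed whatever the baseline category.
- In cohorts of 8, individual listings are readable.
- A clinically significant laboratory change becomes an AE under SAP 12.6, with no condition that the baseline was normal. Protocol 8.7 governs AE monitoring by change from baseline.
- A reader might also infer that dose escalation could be misled. The documents do not support that. Protocol 10.3 bases escalation on review of all available safety data and counts laboratory AEs in the study halting rules. The shift tables belong to the final analysis, after the last participant's last visit (SAP 11.1).
- SAP 12.7 does not say that low and high will be pooled. It only fails to say that they will be separated.

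What survives is narrower. None of these outputs counts category shifts by dose group against placebo for analytes that were abnormal at baseline. The AE route also rests on the same kind of investigator judgement that admitted the out-of-range value.

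**Conclusion.** The point holds as a gap in tabulation, not a loss of data. By its wording, SAP 12.7 covers 2 of 9 category moves and leaves direction unstated, for an outcome that the SAP ranks as primary.

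The 6% to 47% range is the chance that a 6-subject group has at least one subject outside a given analyte's table. It rests wholly on the assumed 1% to 10% rate. It does not measure missed worsening, which is less likely (step 5).

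Two stronger readings should be resisted.

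- **That subjects drop out of the shift tables altogether.** Protocol Table 8 has 28 quantitative blood tests (11 hematology, 14 chemistry without the pregnancy test and FSH, 3 coagulation). If they were independent, 1 − (1 − r)^28 would put 24% (r = 1%) to 95% (r = 10%) of subjects out of range on at least one. But exclusion is per analyte: the same subject is still counted for every test that was normal at baseline. Independence is also doubtful, for example among hemoglobin, hematocrit and red cell count.
- **That these subjects are the ones most likely to worsen, so that a dose-related signal is under-counted.** The documents offer no evidence for this, and regression to the mean would favour movement back toward the range.

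Priority: minor. The reading of SAP 12.7 is secure; its practical effect depends on rates that the documents do not give.

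**What to change.** Reword SAP 12.7 as follows.

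1. For each analyte, tabulate baseline category (low, normal, high) against the worst post-dose category, once toward low and once toward high. For dipstick tests, use normal and the abnormal grades.
2. Include every subject with a baseline and at least one post-dose value, and print the denominator for each dose group and for pooled placebo.
3. Among subjects abnormal at baseline, count those who worsen further by a pre-set amount, such as a multiple of the reference limit or a higher dipstick grade. This is needed because a 3 × 3 table still does not show high to higher.
4. State which visits feed the worst value. SAP section 7 keeps repeat and unscheduled results out of summaries, so either confirm that the rule applies here or make an explicit exception.

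The cost is SAP wording, slightly larger tables and a little more programming. No new data, visits or subjects are needed.
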